**CONFIDENTIAL**

Date:  
Version:  
Status:  
Page:

30 November 2020  
5.0  
Final  
76 of 105

**Novo Nordisk**

### 13.2 Case report form flow

The investigator must ensure that data is recorded in the eCRF as soon as possible, preferably within 5 days after the visit/phone contact. The SMPG measurements and corresponding trial drug doses for titration purpose should be entered within 24 hours after the site visit/phone contact on week days throughout the trial.

Once data has been entered, it will be available to Novo Nordisk for data verification and validation purposes. Queries will be generated in the eCRF, and the investigator should solve these queries on an ongoing basis throughout the trial.

Site specific eCRF data (in an electronic readable format) will be provided to the trial site before access to the eCRF is revoked. This data must be retained at the trial site.

## 14 Monitoring procedures

Monitoring will be conducted using a risk-based approach including risk assessment, monitoring plans, centralised monitoring and visits to trial sites. During the course of the trial, the monitor will visit the trial site to ensure that the protocol is adhered to, that all issues have been recorded, to perform source data verification and to monitor drug accountability. The first monitoring visit will be performed as soon as possible after FSVF at the trial site and no later than 4 weeks after. The monitoring visit intervals will depend on the outcome of the centralised monitoring of the eCRFs (remote assessment of data by Novo Nordisk), the trial site's recruitment rate and the compliance of the trial site to the protocol and GCP.

The monitor must be given direct access to all source documents (original documents, data and records). Direct access includes permission to examine, analyse, verify and reproduce any record(s) and report(s) that are important to the evaluation of the trial. If the electronic medical record does not have a visible audit trail, the investigator must provide the monitor with signed and dated printouts. In addition, the relevant trial site staff should be available for discussions at monitoring visits and between monitoring visits (e.g. by telephone). All data must be verifiable in source documentation other than the eCRF.

For all data recorded the source document must be defined in a source document agreement at each trial site. There must only be one source defined at any time for any data element. Source data generated by the trial site can be corrected by another person than the person entering the source data if accepted by local regulations; any correction must be explained, signed and dated by the person making the correction. The monitor will ensure that the eCRFs are completed and that paper CRFs are collected.

Protocol  
Trial ID: NN1218-4357  
UTN: U1111-1197-8289

**CONFIDENTIAL**

Date:  
Version:  
Status:  
Page:

30 November 2020  
5.0  
Final  
77 of 105

**Novo Nordisk**

The following data will be source data verified for screening failures:

- Date for obtaining informed consent
- Demography
- Screening failure reason
- SAEs, if applicable

Monitors will review the subject's medical records and other source data to ensure consistency and/or identify omissions compared to the eCRF. If discrepancies are found, the investigator must be questioned about these.

Protocol  
Trial ID: NN1218-4357  
UTN: U1111-1197-8289

**CONFIDENTIAL**

Date:  
Version:  
Status:  
Page:

30 November 2020  
5.0  
Final  
78 of 105

**Novo Nordisk**

## 15 Data management

Data management is the responsibility of Novo Nordisk. Data management may be delegated under an agreement of transfer of responsibilities to a CRO.

Appropriate measures, including encryption of data files containing person identifiable data, will be used to ensure confidentiality of subject data, when they are transmitted over open networks.

Data from central laboratories will be transferred electronically. In cases where data is transferred via non-secure electronic networks, data will be encrypted during transfer.

The subject and any biological material obtained from the subject will be identified by subject number and trial ID. Appropriate measures such as encryption or leaving out certain identifiers will be enforced to protect the identity of subjects in all presentations and publications as required by local, regional and national requirements.

## 16 Computerised systems

Novo Nordisk will capture and process clinical data using computerised systems that are described in Novo Nordisk Standard Operating Procedures and IT architecture documentation. The use and control of these systems are documented.

Investigators working on the trial may use their own electronic systems to capture source data.

## 17 Statistical considerations

If necessary, a statistical analysis plan may be written in addition to the protocol, including a more technical and detailed elaboration of the statistical analyses. The statistical analysis plan will be finalised before database lock.

### General considerations

In general, for endpoints evaluated as a change from baseline and/or where a baseline adjustment is made, baseline is defined as information collected at randomisation (V10). In case a measurement is not available at randomisation, the most recent measurement prior to randomisation will be used as baseline.

All efficacy endpoints will be summarised and analysed using the full analysis set (FAS), unless otherwise stated. Safety endpoints will be summarised using the safety analysis set and analysed using the FAS. The FAS is defined in Section [17.2](#).

Presentation of results from a statistical analysis will include the estimated mean treatment effects (LSMeans) for change from baseline, if applicable. Estimated mean treatment differences (or ratios) will be presented together with two-sided 95% confidence interval (CI) for all endpoints analysed statistically.

The primary objective of the trial is to confirm the effect in terms of glycaemic control of treatment with faster aspart compared to NovoRapid® both in combination with insulin degludec with or without metformin in Chinese adults with T1DM or T2DM inadequately treated with a basal-bolus or a premix regimen, using a non-inferiority approach.

More specifically the upper limit of the 95% confidence interval for the difference between faster aspart and NovoRapid® should be compared to a non-inferiority margin of 0.4%. If it is below or equal to 0.4%, non-inferiority will be considered established and effect demonstrated.

### Estimand

The estimand is defined as the treatment difference in change from baseline in HbA1c 16 weeks after randomisation between faster aspart and NovoRapid® both in combination with insulin degludec with or without metformin in Chinese adults with T1DM or T2DM treated on basal-bolus regimen with a basal optimisation if all had adhered to randomised treatment. This estimand aims to reflect the treatment effect for subjects that are actually able to take the drug during the intended treatment period.

#### 17.1 Sample size calculation

The sample size is determined to ensure a sufficient power for the primary analysis. This is determined using a non-inferiority limit of 0.4%.

Protocol  
Trial ID: NN1218-4357  
UTN: U1111-1197-8289

CONFIDENTIAL

Date:  
Version:  
Status:  
Page:

30 November 2020  
5.0  
Final  
80 of 105

Novo Nordisk

In the global phase 3a programme where treatment with faster aspart has been investigated, the completion rates have been high, i.e. approximately 88-94%. Therefore it will not be unexpected that treatment discontinuation might be as low as 10%.

It is expected that a larger portion of the trial population will constitute subjects with T2DM. For these calculations the proportion of subjects with T1DM is assumed to be 20%. Combining expected differences for T1DM and T2DM subjects and weighting by the proportion of expected T1DM subjects we will assume a treatment difference of -0.02% (i.e., in favour of faster aspart).

The power for the primary (non-inferiority) analysis is based on a *t*-statistic under the assumption of a one-sided test of size 2.5 %, a non-inferiority margin of 0.4% and SD of 1.2%. Using these values we get a power of 81.7% for the primary analysis with a sample size of 270. Adjusting further for a dropout rate of approximate 10%, 300 subjects will be randomised.

The power for non-inferiority for scenarios where SD = 1.0% or 1.2% and mean difference of 0.00% or -0.02% based on sample size 270 is shown in Table 17-1.

**Table 17-1 The power for non-inferiority for different scenarios**

Power for non-inferiority	Treatment difference = 0%	Treatment difference = -0.02%
SD = 1.0%	90.6%	93.0%
SD = 1.2%	77.9%	81.7%

The power calculation is done using proc power in SAS Version 9.4.

## 17.2 Definition of analysis sets

The following analysis sets are defined in accordance with the ICH-E9 guidance

- FAS includes all randomised subjects. In exceptional cases, randomised subjects may be excluded from the FAS. In such cases, the reason for exclusion will be justified and documented. Subjects in the FAS will contribute to the evaluation “as randomised”
- Per Protocol (PP) Analysis Set includes all subjects in the FAS, excluding subjects who:
  - Have violated any inclusion criteria
  - Have fulfilled any exclusion criteria
Subjects in the PP analysis set will contribute to the evaluation “as treated”
- Safety Analysis Set includes all subjects receiving at least one dose of randomised treatment. Subjects in the safety analysis set will contribute to the evaluation “as treated”

Protocol  
Trial ID: NN1218-4357  
UTN: U1111-1197-8289

CONFIDENTIAL

Date:  
Version:  
Status:  
Page:

30 November 2020  
5.0  
Final  
81 of 105

Novo Nordisk

Randomised subjects, who are lost to follow-up, and where no exposure information of the trial product or its comparator is available after randomisation, will be handled as unexposed.

Before data are released for statistical review, a blinded review of all data will take place to identify serious non-adherence to the protocol that may potentially affect the results. Furthermore, extreme values and outliers will be identified by the statistician during programming and data review, according to ICH-E9. This will be performed by using a fake randomisation.

The subjects or observations to be excluded, and the reasons for their exclusion must be documented and signed by those responsible before database lock. The subjects and observations excluded from analysis sets, and the reason for this, will be described in the clinical trial report.

### 17.3 Primary endpoint

The primary endpoint is change from baseline (week 0) in HbA1c to 16 weeks after randomisation.

#### Primary analysis:

The estimand will be addressed by the primary analysis on all subjects included in the full analysis set and using the data collected from date of first dose of randomised NovoRapid®/faster aspart and to 7 days after the day of last dose of randomised NovoRapid®/faster aspart. Change from baseline in HbA1c after 16 weeks of randomised treatment will be analysed using a mixed-effect model for repeated measurements (MMRM) where all calculated changes in HbA1c from baseline at visits will be included in the analysis. This model will include treatment and stratification (T1DM/T2DM) as fixed factors, HbA1c at baseline as covariate and interactions between all fixed factors and visit. An unstructured covariance matrix will be used to describe the variability for the repeated measurements for a subject. This approach relies on the assumption that data are missing at random (MAR). From this model, the treatment difference after 16 weeks will be estimated with a 95% confidence interval calculated.

Non-inferiority will be considered confirmed if the upper boundary of the two-sided 95% confidence interval is below or equal to 0.4% or equivalent if the *p*-value for the one-sided test of

$$H_0: D > 0.4\% \text{ against } H_A: D \leq 0.4\%,$$

is less than or equal to 2.5%, where *D* is the mean treatment difference (faster aspart minus NovoRapid®).

The trial also aims to confirm the superiority of treatment with faster aspart for the change from baseline HbA1c 16 weeks after randomisation. Here superiority will be based on the same 95% CI that was used for addressing the primary analysis. Superiority will be confirmed if the upper boundary of the two-sided 95% confidence interval of the mean treatment difference is below 0%.

Protocol  
Trial ID: NN1218-4357  
UTN: U1111-1197-8289

CONFIDENTIAL

Date:  
Version:  
Status:  
Page:

30 November 2020  
5.0  
Final  
82 of 105

Novo Nordisk

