## 5.2 Rationale for trial design

The 8-week run-in period has been included to ensure the subjects are being trained in the trial procedures and that the basal insulin titration is optimised. A 16-week treatment period is needed to obtain valid and adequate efficacy and safety data.

The rationale for the meal test is to evaluate PPG regulation after a standardised meal when injecting faster aspart compared to NovoRapid®.

The treat-to-target approach, and thereby the high frequency of contacts, has been chosen in order to ensure optimal titration of faster aspart and NovoRapid®.

The 7-day follow-up visit, and the 30-day follow up contact are introduced in order to collect information on AEs occurring in the follow-up period.

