### 5.3 Treatment of subjects

At V2, eligible subjects will be enrolled in a run-in period where all subjects will be switched from their pre-trial insulin treatment to basal insulin degludec once daily and bolus insulin NovoRapid® thrice daily as described in the titration guideline (Appendix A1 and A2) with or without metformin.

Subjects with T2DM treated with metformin prior to the trial should continue with their pre-trial dose of metformin. The dose and dosing frequency of metformin should not be changed at any time during the trial, unless due to safety concerns. For T2DM subjects treated with alpha-glucosidase inhibitor, SGLT2i and DPP4i prior to the trial, the OAD(s) must be stopped at the run-in visit (V2). Initiation of any other diabetes treatment is not allowed during the screening, run-in or treatment period and must be reported (see Section 8.2.5). This includes metformin for subjects with T2DM not treated with metformin prior to the trial. During the run-in period, the investigator will focus on optimising the basal insulin treatment using a treat-to-target approach following the titration guideline (Appendix A1 and A2). The bolus insulin will not be titrated during the run-in period unless the investigator finds it necessary to adjust the bolus insulin for safety reasons.

All subjects should consume three main meals (breakfast, lunch and dinner) daily throughout the trial.

In the treatment period, eligible subjects will receive double blinded treatment with either faster aspart or NovoRapid® both in combination with once daily insulin degludec with or without metformin. The investigator should focus on optimising the bolus insulin treatment following the bolus dosing algorithm as described in the titration guideline (Appendix A1 and A2). Surveillance of insulin titration will be performed by Novo Nordisk.

Throughout the trial the bolus insulin (faster aspart or NovoRapid®) should be administered 0-2 minutes prior to the three main meals (i.e. breakfast, lunch and main evening meal). Additional bolus dosing is allowed at the discretion of the investigator.

The maximum duration of treatment will be 24 weeks including the run-in period. No maximum dose is specified. Doses are adjusted according to SMPG values (Appendix A1 and A2).

Use of flash glucose monitoring or a real time continuous glucose monitoring system is not allowed throughout the trial.

Protocol  
Trial ID: NN1218-4357  
UTN: U1111-1197-8289

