### 6.2 Inclusion criteria

For an eligible subject, all inclusion criteria must be answered “yes”.

1. Informed consent obtained before any trial-related activities. Trial-related activities are any procedures that are carried out as part of the trial, including activities to determine suitability for the trial
2. Male or female, age above or equal to 18 years at the time of signing informed consent
3. Diagnosed with T1DM  $\geq$  1 year prior to screening (V1) or diagnosed with T2DM  $\geq$  5 years prior to screening (V1)
4. Treated with a basal-bolus insulin regimen or a premix insulin regimen  $\geq$  1 year prior to the day of screening (V1). Insulin regimen must be unchanged within 60 days prior to screening. A basal-bolus insulin regimen is defined as basal insulin once or twice daily and bolus insulin taken with meals at least thrice daily. A premix insulin regimen is defined as premix insulin twice or thrice-daily
5. For subjects with T1DM: not treated with any OADs for at least 90 days prior to screening (V1).  
For subjects with T2DM: not treated with any OADs or treated with 1-2 OADs within 90 days prior to screening (V1). Allowed OADs are metformin, alpha-glucosidase inhibitor, SGLT2i and DPP4i. Change in OAD and dose is allowed prior to screening
6. HbA1c 7.5-9.5% (both inclusive) as assessed by central laboratory at screening (V1)
7. Able and willing to adhere to the protocol including performance of SMPG profiles and meal tests
8. Able and willing to consume 3 main meals (breakfast, lunch and dinner) daily throughout the trial

The criteria will be assessed at the investigator's discretion unless otherwise stated.

Protocol  
Trial ID: NN1218-4357  
UTN: U1111-1197-8289

CONFIDENTIAL

Date:  
Version:  
Status:  
Page:

30 November 2020  
5.0  
Final  
32 of 105

Novo Nordisk

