4.3.2 Main Analytical Approach

The estimand will be addressed by the primary analysis on all subjects included in the full analysis set and using the data collected from date of first dose of randomised NovoRapid®/faster aspart and to 7 days after the day of last dose of randomised NovoRapid®/faster aspart. Change from baseline in HbA_{1c} after 16 weeks of randomised treatment will be analysed using a mixed-effect model for repeated measurements (MMRM) where all calculated changes in HbA_{1c} from baseline at visits will be included in the analysis. This model will include treatment and stratification (T1DM/T2DM) as

fixed factors, HbA_{1c} at baseline as covariate and interactions between all fixed factors and visit. An unstructured covariance matrix will be used to describe the variability for the repeated measurements for a subject. This approach relies on the assumption that data are missing at random (MAR). From this model, the treatment difference after 16 weeks will be estimated with a 95% confidence interval calculated.

Non-inferiority will be considered confirmed if the upper boundary of the two-sided 95% confidence interval is below or equal to 0.4% or equivalent if the *p*-value for the one-sided test of $H_0: D > 0.4\%$ against $H_A: D \leq 0.4\%$,

is less than or equal to 2.5%, where D is the mean treatment difference (faster aspart minus NovoRapid®).

The trial also aims to confirm the superiority of treatment with faster aspart for the change from baseline HbA_{1c} 16 weeks after randomisation. Here superiority will be based on the same 95% CI that was used for addressing the primary analysis. Superiority will be confirmed if the upper boundary of the two-sided 95% confidence interval of the mean treatment difference is below 0%.

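### The primary MMRM omits screening (V1) HbA1c, which may add a little precision because V10 HbA1c follows 8 weeks of changing therapy

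*Protocol*

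**What the plan says.** **Model.** Protocol 17.3: "This model will include treatment and stratification (T1DM/T2DM) as fixed factors". Baseline HbA1c is the single covariate, fixed factors interact with visit, and the covariance is unstructured. SAP 4.3.2 repeats this ("This model will include treatment and stratification (T1DM/T2DM) as" fixed factors), and SAP 4.5 records no change from the protocol. The tipping-point and per-protocol analyses build on the same model.

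**Baseline.** Protocol 4.2 sets baseline at V10, week 0.

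**What happens before V10.** Protocol 5.2 explains the period: "The 8-week run-in period has been included to ensure the subjects are being trained in the trial procedures and that the basal insulin titration is" (the sentence closes by naming optimisation as the aim). Under Protocol 5.3 all subjects switch at V2 to degludec plus NovoRapid. For T2DM subjects on an alpha-glucosidase inhibitor, SGLT2i or DPP4i, "the OAD(s) must be stopped at the run-in visit (V2"). Section 3.2.1 of Appendices A1 and A2 has degludec adjusted weekly from Visit 2 to Visit 9.

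**What is already measured.** Inclusion criterion 6 (Protocol 6.2) requires HbA1c of 7.5 to 9.5% ("both inclusive) as assessed by central laboratory at screening (V1"). Every properly enrolled subject therefore has a central-laboratory HbA1c from before the run-in. FPG at baseline is needed for a supportive secondary endpoint, and HbA1c is also measured at V9.

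**The concern.** Protocol 3.2 describes HbA1c as a measure of long-term control. If it averages glucose over a period longer than the run-in, or comparable with it, V10 HbA1c mixes glucose from before V2, from the titration weeks and from the level finally reached. Two subjects with the same V10 value could be moving in opposite directions: one falling after basal optimisation, one rising after losing an oral agent. Part of the later change would then be run-in carry-over that V10 HbA1c alone cannot separate. V1 HbA1c, taken together with V10 HbA1c, gives a rough slope.

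Randomisation balances this carry-over between arms, so it cannot distort the treatment difference. It can only add residual variance and widen the confidence interval that is compared with 0.4% for non-inferiority and with 0% for superiority.

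**Working it through.** **Step 1: reproduce the plan's power.** Protocol 17.1 gives a "one-sided test of size 2.5 %, a non-inferiority margin of 0.4% and SD of 1.2"%, says "we will assume a treatment difference of -0.02% (i.e., in favour of faster aspart"), and reports "power of 81.7% for the primary analysis with a sample size of 270". Allocation is 1:1, so 135 per arm.

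- SE = SD × √(4/N) = 1.2 × √(4/270) = 0.1461
- Noncentrality = (0.4 + 0.02)/0.1461 = 2.876, with 268 df
- Noncentral t power = 81.73% (stated 81.7%)
- 95% CI half-width = 1.969 × 0.1461 = 0.288

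The other three cells of Table 17-1 also reproduce (90.6%, 93.0%, 77.9%), and 270/0.9 = 300. The sample size is not in error.

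**Step 2: effect of a variance cut.** Let r² be the share of the remaining week-16 variance that an added covariate explains. The residual SD becomes 1.2 × √(1 − r²). The documents do not give r², so it is shown as a range.

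| r² | Residual SD | CI half-width | Power, difference -0.02 | Power, difference 0 |
|---|---|---|---|---|
| 0 | 1.200 | 0.288 | 81.7% | 77.9% |
| 0.01 | 1.194 | 0.286 | 82.1% | 78.3% |
| 0.02 | 1.188 | 0.285 | 82.5% | 78.7% |
| 0.05 | 1.170 | 0.280 | 83.6% | 80.0% |
| 0.09 | 1.145 | 0.274 | 85.2% | 81.6% |

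**Step 3: is there a lag at V10?** The documents give no HbA1c kinetics. As an illustration, assume a weight on past glucose that falls linearly to zero over 120 days.

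- Share of V10 HbA1c from before V2 (56 days earlier): (64/120)² = 28%
- Glucose steps at V2 (regimen switch, oral agent stopped): 1 − 28% = 72% of the change is already in V10 HbA1c
- Glucose drifts linearly over the 56 days (gradual titration): (2/120²) × (120×56 − 56²/2 − 120×56/2 + 56²/3) = 39% is in V10 HbA1c

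The true course is a mixture, because the switch is abrupt and the titration gradual.

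**Step 4: plausible r².** A simulation with every input assumed used:

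- exponential HbA1c memory of 3, 4 or 6 weeks;
- linear change over the run-in;
- pre-trial SD 0.7 and assay SD 0.15;
- end-of-run-in level = ρ × pre-trial level + noise, with (ρ, noise SD) of (0.9, 0.4), (0.6, 0.6) or (0.4, 0.8);
- week-16 level = 0.6 × end-of-run-in level + noise of the same SD.

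Results:

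- V1 HbA1c added to V10 HbA1c: r² from 0.4% to 7.5%
- V10 FPG added as well: r² from 0.5% to 8.5%, so FPG contributes at most about 1.4 percentage points

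Other assumed shapes gave about 0.1–2% for a step at V2 and about 0.5–4.5% for linear drift when half of it persists to week 16. They gave 8–14% only with full persistence and a large run-in shift.

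**Caveat on scale.** In the widest scenario above, the total week-16 variance is 0.36 × (0.16 × 0.49 + 0.64) + 0.64 + 0.0225 = 0.92, an SD of 0.96. Applying its r² to an SD of 1.2 therefore tends to flatter the gain.

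**The case against.** The strongest reply is that nothing here is wrong. The baseline value plus the stratification factor is a complete, pre-specified model. The estimate is unbiased, and an extra covariate is optional. That stands, and it limits the point to a low-cost improvement.

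Several arguments also hold the size down, and they stand too:

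- Two of the drivers (regimen switch, oral-agent withdrawal) act at V2, so much of their effect may have reached HbA1c by V10.
- Bolus insulin is titrated weekly for 16 weeks toward a common 4.0–6.0 mmol/L target, which works to erase each subject's end-of-run-in level.
- Oral-agent withdrawal concerns T2DM only, so the stratum term already absorbs part of any difference in drift.
- The documents do not say whether SD 1.2 is before or after baseline adjustment. If before, the planned power is already conservative.

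A reader might infer more than the documents support. They do not state that HbA1c is still moving at V10; that is an inference from the design. Nor do they support a firm loss of precision, or variance cuts well above 10%, which need near-full persistence of a large run-in shift. A reader might also want V10 FPG as a required covariate. But the run-in titrates toward pre-breakfast values of 4.0–5.0 mmol/L, and the V10 meal test starts only with SMPG of 4.0–8.8 mmol/L (Protocol 8.3.1). If FPG is drawn at that visit, its spread is compressed, which fits its small contribution in the simulation.

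What the objection does not remove is the asymmetry: V1 HbA1c is already in the database for every subject, and including it costs almost nothing even if r² is close to zero.

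**Conclusion.** The point holds as a minor efficiency improvement. The primary model uses one glycaemic baseline value, taken after 8 weeks of changing therapy, and leaves out a pre-run-in value that is already collected. Treatment estimate, alpha and stated power are all sound.

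The gain depends on an r² that the documents do not supply. From under 1% to about 9% is plausible, giving power of about 82% to 85% against 81.7%, with 0 to 3 points most likely. The half-width would narrow from 0.288 to no less than about 0.274. If the true difference is 0, the same range takes power from 77.9% to at most about 81.6%. These figures assume some lag at V10, some persistence of run-in differences to week 16, and a residual SD of 1.2. It would be wrong to conclude that the trial is underpowered on its own assumptions, or that the non-inferiority result would be compromised without the change.

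**What to change.** - In Protocol 17.3 and SAP 4.3.2, add screening (V1) HbA1c as a continuous covariate with its own visit interaction, alongside V10 HbA1c.
- Carry the same term into both tipping-point analyses (including the imputation model), the per-protocol analysis and the T1DM/T2DM estimates, so that all stay comparable with the primary result.
- Several secondary endpoints use a model described as similar to the primary one. State that the new term applies to the HbA1c models only.
- Update SAP 4.5, which now records no change, and finalise before database lock and unblinding.
- V10 FPG may be added but is optional. If it is, a rule for missing values is needed. V1 HbA1c should be complete because eligibility depends on it; one line can cover any exception.

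Cost: SAP wording, no new data, and about one degree of freedom per visit. If the sponsor prefers to leave the primary model untouched, the same model could be pre-specified as a supportive analysis, but the precision would then not count toward the primary conclusion.
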